5.3. Criteria to be Confirmed Prior to Commencing OLE at Visit 11 criteria

Patients who complete the DB period of the study on treatment may be eligible to continue into the OLE.

5.4. Lifestyle restrictions

1. Fertile and sexually active female patients should use effective contraceptive methods throughout the study and 12 weeks after last dose of the IP.
2. Patients must abstain from donating blood, plasma, or platelets from the time of informed consent, to 12 weeks after last dose of the IP.

5.5. Screen failures

Screen failures are defined as patients who signed the informed consent form to participate in the clinical study but are not subsequently randomised and must not be assigned to the study treatment. These patients must be withdrawn from the study. A minimal set of screen failure information is required to ensure transparent reporting of screen failure patients to meet the Consolidated Standards of Reporting Trials publishing requirements and to respond to queries from regulatory authorities. Minimal information includes demography, screen failure details, eligibility criteria, and any serious adverse event (SAE).

These patients should have the reason for study withdrawal recorded in the electronic case report form (eCRF) as “Incorrect Enrolment” (i.e.. Patient does not meet the required inclusion/exclusion criteria). This reason for study withdrawal is only valid for screen failures (not randomised patients).

5.5.1. Re-screening

Re-screening is allowed only once for a patient. In case that patients are screening failed due to Civil Crisis, Natural Disaster, or Public Health Crisis at the first rescreening, second rescreening is allowed.

Rescreening and/or up to 6-week extension of the screening period, is allowed for transient reasons (including but not limited to equipment/procedure failure, e.g. problems with the ePRO device impacting availability of data, or unforeseen personal events that result in a missed visit).

For patients who require SCS for an asthma exacerbation or worsening of nasal polyp symptoms during the screening period (prior to V2), the screening period may be extended, provided the treatment duration with SCS is ≤ 17 days. The next regular study visit (Visit 2) will be delayed and may proceed no sooner than 4 weeks after the last dose of SCS.

Extension of the screening period can be allowed if deemed necessary by the investigator and agreed with the AZ study physician/delegate (e.g. in case of acute events, or need to obtain additional evidence of the patient's eligibility).

If the duration of treatment with SCS is >17 days, or SCS is used at or after V2, patients should be screen failed, but can be considered for re-screening.

Patients who fail to meet the required total NP score at V1 or V2, may be considered for re-screening once an appropriate time interval, as deemed by the investigator, has elapsed.

Patients may not be re-screened or have an extended screening period for failure to meet minimum symptom severity or SinoNasal Outcome Test (SNOT-22) requirements.

Re-screened patients should be assigned the same patient number as for the initial screening. It means that patient should keep the same E-code as was originally assigned. For second rescreening, the patient will be assigned new E-code.

Re-screened patients should re-sign informed consent. All procedures from the screening/run-in period should be repeated. CT will be repeated at rescreening if it has been more than 3 months since the previous scan at screening; or repeated earlier at the discretion of PI. Re-screening should be documented so that its effect on study results, if any, can be assessed.

6. STUDY TREATMENTS

Study treatment is defined as any investigational product(s) (including marketed product comparator and placebo) or medical device(s) intended to be administered to a study participant according to the study protocol. Study treatment in this study refers to benralizumab 30 mg or matching placebo, 1 mL.

6.1. Treatments administered

6.1.1. Investigational products

Table 6 Study Treatments

	Treatment 1	Treatment 2
Study treatment name:	Benralizumab	Placebo
Dosage formulation:	30 mg/mL solution for injection in accessorized pre-filled syringe, 1 mL fill volume	Matching placebo solution for injection in accessorized pre-filled syringe, 1 mL fill volume
	Clear to opalescent, colourless to yellow solution.	Clear to opalescent, colourless to yellow solution.
Route of administration	subcutaneously	subcutaneously
Dosing instructions: Also refer to Section 6.2 of study specific handling instructions are required i.e. for IV preparation	Benralizumab active solution will be administered subcutaneously to patients by health care professionals, patients, or their caregivers using an accessorized prefilled syringe (APFS). Each prefilled syringe is designated for single use only and is not to be administered to more than one patient.	Placebo solution will be administered subcutaneously to patients by health care professionals in this clinical study using an accessorized prefilled syringe (APFS). Each prefilled syringe is designated for single use only and is not to be administered to more than one patient.
Packaging and labelling	Study treatment will be provided in accessorized pre-filled syringe. Each syringe will be labelled in accordance with Good Manufacturing Practice (GMP) Annex 13 and per country regulatory requirement. Label text will be translated into local language as required. The label will include the following information: 
 • Study code Investigational product/study treatment dosage form, route of administration, and quantity of dosage units 
 • Kit ID • P Lot ID • Expiry date • Investigator Name (to be written on the label) • E-code (to be written on the label) 	Study treatment will be provided in accessorized pre-filled syringe. Each syringe will be labelled in accordance with Good Manufacturing Practice (GMP) Annex 13 and per country regulatory requirement. Label text will be translated into local language as required. The label will include the following information: 
 • Study code Investigational product/study treatment dosage form, route of administration, and quantity of dosage units 
 • Kit ID • P Lot ID • Expiry date • Investigator Name (to be written on the label)

	
 • Sponsor name and contact details • Directions for use • Storage condition • Standard statements required by regulatory authorities 	
 • E-code (to be written on the label) • Sponsor name and contact details • Directions for use • Storage condition • Standard statements required by regulatory authorities
Provider	AstraZeneca	AstraZeneca

6.2. Preparation/handling/storage/accountability

6.2.1. Preparation and handling

Up to and including on Visit 12, the investigational product will be administered at the study site on treatment visits and within visit windows as specified in the SoA. After Visit 12, IP may be administered within the visit windows as described in Table 3, either on-site by an HCP or, optionally, at home or a remote location by the patient or their caregiver. Self-administration of the IP requires assessment and training by the Investigator (Section 6.2.1.X).

The Investigator or designee must confirm appropriate temperature conditions have been maintained during transit and storage for all study treatment received and any discrepancies are reported and resolved before use of the study treatment.

Only patients enrolled in the study may receive study treatment and only authorised site staff may supply or administer study treatment.

Before investigational product administration

Prior to each IP administration:

- Investigator/authorized delegate will assess injection site as per standards of medical care;
- For WOCBP, urine pregnancy test will be done; IP will be administered only when the result of the test is negative.

Investigational product administration

The investigational product will be administered by the Investigator/authorized delegate. Investigational product should be administered into the upper arm, thighs, or the abdomen (see [Figure 2](#)).

It is recommended that the site of injection is rotated such that the patient receives IP at a different anatomical site at each treatment visit. Investigational product should not be administered into areas where the skin is tender, bruised, erythematous, or hardened.

Figure 2 Injection Sites Scheme

Further details on IP administration are described in the IP Handling Instruction provided to study sites. Investigational product administration must be carried out in line with the Instruction.

After investigational product administration

After IP administration, the patient should be observed in case of any acute drug reactions in line with clinical practice.

Conditions requiring investigational product administration rescheduling

If any of the following occur, the Investigator should reschedule the visit and the IP should not be administered until the rescheduled visit:

- The patient has an intercurrent illness, that in the opinion of the Investigator may compromise the safety of the patient in the study (e.g. viral illnesses).
- The patient, in the opinion of the Investigator, is experiencing an acute or emerging asthma exacerbation.
- The patient is febrile ($\geq 38^{\circ}\text{C}$; $\geq 100.4^{\circ}\text{F}$) within 72 hours prior to the IP administration.

6.2.2. Self-administration of Investigational Product as Mitigation to Disruption

At Visits 3 and 4, appropriate patients and/or their caregiver may be trained in self-administration of investigational product administration by the investigator or designee. If not

possible at Visits 3 and 4, this may occur at later visits. This training will be provided so that patients are prepared in case remote visits may be required secondary to study disruptions as described in Section 4.1.1. Patients may still participate in the study if they do not consent/assent to this training.

6.2.3. Optional At-home or Remote Location Self-administration

To reduce patient burden and to allow flexibility during the OLE, patients will have the option for at-home or remote location self-administration of IP, or at-home or remote location administration of IP by the patient's caregiver using the APFS. The investigator will first assess the patient and/or his/her caregiver to ensure they are appropriate for self-administration of IP, or caregiver administration of IP, and have received appropriate training. All necessary supplies and instructions for administration and documentation of IP administration will be provided.

If the IP is administered at the patient's home/remotely, the patient should administer the IP the same day as the Visit, after the visit assessments. It is strongly encouraged that the patient is contacted by the Investigator or qualified designee after the dose is administered in line with clinical practice. If the patient reports an injection site reaction or other AEs, the Investigator or qualified designee will complete the AE eCRF page and additional eCRF questions about the injection site reaction or other AEs.

Refer to the Study Instructions for At-home or Remote Location Administration of Benralizumab by the Patient and/or His/Her Caregiver for step-by-step guidance including Investigator assessment/training of patient and/or caregiver, drug accountability, and reconciliation requirements. The option of at-home or remote-location administration of IP will only be available in countries where allowed according to local regulations.

6.2.4. Optional Remote Visits for Patients Doing At-Home or Remote-Location

Investigational Product Administration

During the OLE, some visits (as specified in the SoA in Section 1.1) can optionally be done as remote visits by telephone contact for patients who are doing at-home/remote-location IP administration.

For these patients, IP kits and (for WOCBP) urine dipsticks for pregnancy testing for the optional remote visits will be dispensed at the prior, mandatory on-site visit during OLE. WOCBP should be asked if they are pregnant during the telephone visit.

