Visit window ^{a)}	±7 days										
Safety Assessments											
Brief physical examination ^{b)}	X			X					X		8.2.2.2
Vital signs ^{b)}	X			X					X		8.2.3
Adverse events	X	X	X	X	X	X	X	X	X	X	8.3, Appendix B
Concomitant medications	X	X	X	X	X	X	X	X	X	X	6.5
HRU Assessment											
Asthma exacerbation	X	X	X	X	X	X	X	X	X	X	8.1.1.6
Nasal polyps assessments											
Assess nasal surgery or/and SCS use	X	X	X	X	X	X	X	X	X	X	8.1.4, 8.1.5, 6.5
Laboratory Assessments											
Urinary pregnancy test ^{e)}	X	X	X	X	X	X	X	X	X	X	5.1, 8.2.1.1
Clinical chemistry				X					X		8.2.1
Haematology				X					X		8.2.1
PK ^{e)}				X					X		8.5
Immunogenicity ^{e)}				X					X		8.6
Investigational Product Administration											
Investigational Product dispensed and administration ^{f)}	X ^{g)}	X	X	X	X	X	X	X	X	X	6.1, 6.2

- a. All visits to be scheduled from the date of randomization, not from the date of previous visit, except for early discontinuation from IP.
- b. Visit 13, 14, 16, 17 and 18 can optionally be performed via telephone/virtual system based upon the judgement of the PI and patient. This includes self-administration of IP at home.
- c. For patients who prematurely discontinue IP should return to the study site and complete the procedures described within 8 weeks after the last dose of IP.
- d. Unscheduled visits may be initiated as needed, and additional assessments may be performed at these visits as indicated.

- e. At dosing visits, must be collected pre-dose.
- f. IP administration should be the last activity of the visit. All visit procedures should be done prior to dosing.
- g. Patients who are assigned to benralizumab arm will have a placebo injection.

FU- Follow-up; HRU- Healthcare resource utilization; IPD- Investigational product discontinuation; PK- Pharmacokinetics; SCS- Systemic corticosteroids; UNS- Unscheduled.

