8. STUDY ASSESSMENTS AND PROCEDURES

Study procedures and their timing are summarised in the [SoA](#).

The investigator will ensure that data are recorded on the eCRF. Medidata Web Based Data Capture system will be used for data collection and query handling.

The investigator ensures the accuracy and completeness of the eCRFs including: the legibility and timeliness of the data recorded and of the provision of answers to data queries according to the Clinical Study Agreement. The investigator will sign the completed eCRF. A copy of the completed eCRF will be archived at the study site.

Safety concerns should be discussed with the sponsor immediately upon occurrence or awareness to determine if the patient should continue or discontinue study treatment.

Adherence to the study design requirements, including those specified in the SoA, is essential and required for study conduct.

All screening evaluations must be completed and reviewed to confirm that potential patients meet all eligibility criteria. The investigator will maintain a screening log to record details of all patients screened and to confirm eligibility or record reasons for screening failure, as applicable.

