8.2.1.1. Pregnancy test

The following tests are applicable to female patients only and will be conducted in accordance with the schedules provided in the [SoA](#).

- Serum beta-HCG: To be performed for all females at screening Visit 1 except for those who are NOT of child bearing potential as defined in inclusion criterion 23. This test is to be sent to and analysed at the central laboratory;
- FSH: To be performed at screening Visit 1 only, at the central laboratory, for female patients to confirm postmenopausal status in women <50 years who have been amenorrhic for >12 months;
- Urine HCG: To be performed at the study site for all females at each treatment visit before IP administration using a dipstick except for those females who are NOT of child bearing potential as defined in inclusion criterion 14. Serum pregnancy test could be used to replace Urine HCG, per local site/lab practice.
 WOCBP who are doing optional remote visits with IP self-administration (after Visit 12) will be provided with urine pregnancy dipstick test and advised to perform the test prior to IP self-administration. If the urine pregnancy test result is positive, the patient should contact the site and should not administer IP.
 A positive urine test result must be confirmed with serum beta-HCG.

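### For remote doses in the open-label extension, the protocol states the pre-dose pregnancy test more weakly than its own general rule and does not tell the site to obtain the home result

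*Protocol*

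**What the plan says.** The general rule is firm:

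- Protocol 6.2.1 opens by allowing doses after Visit 12 to be given "either on-site by an HCP or, optionally, at home or a remote location by the patient or their caregiver". In its list of steps before each administration it then states: "For WOCBP, urine pregnancy test will be done; IP will be administered only when the result of the test is negative". Section 6.4 repeats the negative-result condition for rescheduled doses.
- Protocol Table 3 marks the urine test at every OLE visit, including V13, V14, V16, V17 and V18, which footnote b allows to be held by telephone or virtual system with self-administration at home. Footnote f puts all visit procedures before dosing. As extracted, the test row also carries footnote e, "At dosing visits, must be collected pre-dose".
- Protocol Section 8 makes the schedule binding: "Adherence to the study design requirements, including those specified in the SoA, is essential and required for study conduct".
- Protocol 8.2.1.1 gives the standard test as "To be performed at the study site for all females at each treatment visit before IP administration using a dipstick".

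The text specific to remote visits is softer:

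- Protocol 8.2.1.1 says that WOCBP who self-administer at remote visits receive a dipstick and are "advised to perform the test prior to IP self-administration". The stop rule that follows is: "If the urine pregnancy test result is positive, the patient should contact the site and should not administer IP".
- Protocol 6.2.4 has dipsticks handed out at the preceding on-site visit and adds: "WOCBP should be asked if they are pregnant during the telephone visit". It gives no instruction about the dipstick result.
- Protocol 6.2.3 places the home dose on the day of the visit, after the assessments, and refers sites to separate instructions for at-home dosing, which are not among the documents.

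**The concern.** A rule to dose only on a negative test and a rule not to dose on a positive test differ in one case: the test that was not done. Staff running a telephone visit will naturally turn to the passages written for it, and those carry the weaker rule.

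The telephone question does not close that gap. A dipstick is there to find a pregnancy the woman does not know about, and asking her whether she is pregnant cannot do that. Asking for the result would at least show that a scheduled test had been missed. Section 8.4.2.1 requires IP to stop immediately on pregnancy, so what is at stake is avoidable exposure early in an unrecognised pregnancy.

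**Working it through.** This is mainly a comparison of texts. The plan gives no figure to reproduce.

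**Step 1. Apply each rule to the three possible states of the home test.**

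| Home dipstick | 6.2.1 (and 6.4 for rescheduled doses) | 8.2.1.1, remote sentences alone |
|---|---|---|
| Negative | Dose | Dose |
| Positive | No dose | No dose, contact site |
| Not done | No dose | Dose not barred |

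The rules part only in the last row. Table 3 requires the test and footnote f puts it before the dose, but Table 3 does not mention a negative result; that condition comes from 6.2.1 and 6.4. The superscripts were read imperfectly from the PDF, so nothing here depends on footnote e.

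**Step 2. Is the site told to obtain the result?** Sections 6.2.3, 6.2.4, 6.4 and 8.2.1.1 and Table 3 contain no express instruction to obtain, confirm or record the home result before a remote dose.

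**Step 3. How many doses can be affected?** OLE doses fall at Weeks 56, 60, 64, 72, 80, 88, 96 and 104, which is 8. Those that may be remote are Weeks 64, 72, 88, 96 and 104, which is 5. 5/8 = 62.5%.

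**Step 4. For how long is a home test the first screen?** Count from the on-site test at Week 60:

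- Intervals that end in a possible home test: (64−60) + (72−64) + (88−80) + (96−88) + (104−96) = 36 weeks.
- Interval that ends in the on-site test at V15: 80−72 = 8 weeks.
- Total: 36 + 8 = 44 weeks.

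For a woman who takes every remote visit, a home test is therefore the first to screen new conceptions in 36 of 44 weeks.

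**Step 5. Order of magnitude only.** The documents give neither the number of WOCBP in the OLE, nor remote uptake, nor the rate of skipped tests. Assume 40 to 60 women, all taking every remote visit, and 10% to 30% of home tests skipped. Take 1% per year as the conception rate; inclusion criterion 17 describes highly effective contraception as failing in less than 1% per year under consistent and correct use.

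- Remote doses: 40 × 5 = 200 to 60 × 5 = 300.
- Exposure: 36/52.18 = 0.690 years per woman.
- Conceptions in those weeks: 40 × 0.01 × 0.690 = 0.276 to 60 × 0.01 × 0.690 = 0.414.
- Pregnancies dosed because a test was skipped: 0.276 × 0.10 = 0.028 to 0.414 × 0.30 = 0.124.

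These figures are neither an estimate nor a bound. Imperfect contraceptive use would raise them, and partial remote uptake would lower them. They show only that the expected count is small under these assumptions.

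**The case against.** The strongest reply is that the requirement is already in place. Table 3 schedules the test at the remote visits, footnote f and 6.2.3 put it before the dose, and Section 8 makes the schedule binding. Read together, a skipped home test is a protocol departure. This stands. A reader might infer from 8.2.1.1 that the test is waived or optional for remote doses; the documents as a whole do not support that.

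It can also be argued that 6.2.1 is on-site language, since the same part has the investigator or delegate inspect the injection site and give the dose. On that reading 8.2.1.1 is the remote rule and there is no direct clash over the negative result. That reading is possible, but the opening of 6.2.1 covers home dosing expressly. If 6.2.1 did not reach remote doses, a negative result would not be an explicit condition for them, which leaves the same gap.

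A reader might also infer from 6.2.4 that sites do not collect the dipstick result, or that the question replaces the test. Neither follows. Section 6.2.4 is silent on the result, it dispenses dipsticks for these same visits, the investigator has a general duty under Section 8 to see that data are recorded, and the separate at-home instructions may ask for the result. Those instructions could close the operational gap, but they would not remove the uneven wording in the protocol.

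Finally, the size is negligible and its inputs are assumed. This is conceded, and it is why the point is minor.

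**Conclusion.** The point holds as a minor inconsistency of wording on a dosing precondition. The remote-visit sentences in 8.2.1.1, taken alone, leave an untested woman free to dose, where 6.2.1 would not; and 6.2.4 does not have the site ask for the one fact that would reveal a skipped test. The gap is limited to an untested woman or an unreported result, at up to 5 of 8 OLE doses. It does not extend to dosing after a known positive, which 8.2.1.1 already forbids.

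The expected harm is very small. The documents do not allow a reliable figure, and the contraceptive failure rate in inclusion criterion 17 should not be read as an upper limit, because it is conditional on consistent and correct use. No efficacy analysis is affected. The conclusion rests on the protocol text alone; the at-home instructions were not available.

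**What to change.** Two edits to the Protocol:

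- In 8.2.1.1, replace "advised to perform the test prior to IP self-administration" with: *must perform the test before self-administration and may self-administer IP only if it is negative*. This brings it into line with 6.2.1.
- In 6.2.4, keep the pregnancy question and add that the site asks for and records the dipstick date and result during the remote visit, before the dose.

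The cost is one recorded item per remote visit, if it is not already captured, and a protocol amendment. Appendix A 1 requires ethics approval for amendments, here across about 12 countries and 115 sites, so the change is best bundled with the next one. No new procedure is needed, because the dipsticks are already dispensed and the visit assessments already precede the dose. The result stays self-reported: the change would expose a skipped test but would not verify the reading.
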